5.1.2 Secondary analysis of primary outcome

The difference between treatment group means at week 6 will be estimated using analysis of covariance (ANCOVA), adjusting for baseline OMWQ-HN. This will be on a complete case basis for those participants with a score at both baseline and 6 week visit. If the assumptions of the ANCOVA model are satisfied an adjusted mean difference between treatment groups at week 6 with 95% CI will be reported. This analysis is equivalent to analysing the change from baseline adjusted for baseline. The baseline and week 6 OMWQ-HN data will be presented graphically:

Example Figure 5: Spaghetti plot, OMWQ-HN score: change from baseline to week 6

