5. ANALYSIS METHODS

5.1 Primary outcome

Definition of the primary outcome:

The primary outcome is the OMWQ-HN score at week 6 following start of LLLT treatment.

Primary outcome measure

The primary outcome measure is the OMWQ-HN score. The OMWQ-HN was collected at baseline, weekly during weeks 1 to 6 of treatment, and at 4 month follow-up.

[figure not shown]
Responses to the OMWQ-HN will be summed to give a total overall score between 0 and 54 (a higher score indicating poorer wellbeing and oral function). The total score will not be computed for participants who had missing data on ≥ 1 item, with the exception of participants who scored '0' (=no soreness) on question 1 (who would not then proceed to the remaining questions and would be given a total score of 0).

Example Table 8: Completeness of primary outcome data by visit and treatment group

	Laser			Sham			Total					
	n	Fully missing	Partial missing	Complete	n	Fully missing	Partial missing	Complete	n	Fully missing	Partial missing	Complete
Baseline												
Week 1												
Week 2												
Week 3												
Week 4												
Week 5												
Week 6												
4 month												

The OMWQ-HN will be explored graphically using individual participant plots over time and at 6 weeks using histograms or dotplots and/or boxplots by treatment group. The OMWQ-HN will be summarised numerically as mean, standard deviation, median, interquartile range, and range at each time point for each of the treatment groups.

Example Figure 4: Individual participant plots of OMWQ-HN by visit [baseline to week 6]

Example Table 9: Summary statistics for OMWQ-HN over time

Laser								
	Baseline (n =)	Week 1 (n =)	Week 2 (n =)	Week 3 (n =)	Week 4 (n =)	Week 5 (n =)	Week 6 (n =)	4 Month (n =)
Min								
Median (IQR)								
Mean (SD)								
Max								
Sham								
	Baseline (n =)	Week 1 (n =)	Week 2 (n =)	Week 3 (n =)	Week 4 (n =)	Week 5 (n =)	Week 6 (n =)	4 Month (n =)
Min								
Median (IQR)								
Mean (SD)								
Max								
Higher scores on the OMWQ-HN indicate poorer wellbeing and oral function.								

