5.1.1 Primary analysis of primary outcome

The difference between treatment group means at week 6 will be reported with 95% confidence interval.

Example Table 10: Mean difference in OMWQ-HN at 6 weeks between treatment groups

[figure not shown]
OMWQ-HN at week 6 Mean(sd)		Difference in means (95% CI) (Sham minus Laser)
Sham (n=)	Laser (n=)	
		Mean diff (95% CI)

(a higher score indicates poorer wellbeing and oral function)

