Data on the global, emotional, functional, physical, and total/composite scores will be summarised descriptively as mean, standard deviation, median, interquartile range and range at each time point for each of the treatment groups. The difference between treatment group mean total/composite score and mean global score at week 6 adjusted for the baseline of the score will be reported with 95% confidence intervals (only if the assumptions of the ANCOVA model are satisfied). This will be on a complete case basis for those participants with a score at both baseline and 6 week visit. A 95% confidence interval for the difference at 4 months will be reported if appropriate.

EORTC-QLQ-C30 (version 3.0) and EORTC-QLQ-H&N35 (version 3.0):

Procedures for scoring the scales and items of the QLQ-C30 and H&N35 will be in accordance with the published scoring manual [6]. Therefore, a scale’s score will only be calculated if at least half of its items are non-missing. The QLQ-C30 summary score will be computed as the mean of 13 scores from the QLQ-C30 (excluding the global health/QoL and financial difficulties scores) [7]. The symptom scales/items that form part of the summary score will be reverse scored first to ensure that higher scores on the summary score reflect better outcomes.

Data on the 21 outcome measures will be summarised descriptively as mean, standard deviation, median, interquartile range and range at each time point for each of the treatment groups. The difference between treatment group means for each of the 21 outcome measures at week 6 adjusted for the baseline of the outcome measure will be reported with 95% confidence intervals (only if the assumptions of the ANCOVA model are satisfied). This will be on a complete case basis (after pro-rating) for those participants with a score at both baseline and 6 week visit. A 95% confidence interval for the difference at 4 months will also be reported if appropriate.

Performance Status Scale for Head and Neck Cancer patients (PSS-HN):

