5.5 Missing data

Statistical analyses will be conducted on complete cases from the mITT analysis set. Participants will be included in analyses if they attended the visit of interest and had evaluable data for the outcome measure of interest. Evaluable data here is non-missing for all outcome measures listed in Section 2.4 except the three questionnaires MDADI, QLQ-C30 and H&N 35, where simple imputation for missing questionnaire items in accordance with the questionnaire's scoring manual will be used.

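### The adjusted analyses in SAP 5.1.2 and 5.2 drop participants who have a week-6 score but no baseline score; keeping them is free and gives a modest gain in precision if any baselines are missing

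*SAP*

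**What the plan says.** The primary analysis (SAP 5.1.1) is unadjusted and needs only a week-6 score: "The difference between treatment group means at week 6 will be reported with 95% confidence interval".

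The secondary analysis of the same outcome (SAP 5.1.2) is "estimated using analysis of covariance (ANCOVA), adjusting for baseline OMWQ-HN", and its population is narrower: "This will be on a complete case basis for those participants with a score at both baseline and 6 week visit". Section 5.2 applies the same restriction to the MDADI composite and global scores. For the 21 QLQ-C30 and H&N35 measures it reads: "This will be on a complete case basis (after pro-rating) for those participants with a score at both baseline and 6 week visit".

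Section 5.5, in line with 3.2, gives the general rule: "Statistical analyses will be conducted on complete cases from the mITT analysis set". The only imputation allowed is at item level, for MDADI, QLQ-C30 and H&N35. Nothing covers a baseline score that is missing altogether. For OMWQ-HN there is no item-level rescue either: "The total score will not be computed for participants who had missing data on ≥ 1 item", unless question 1 was answered 0. Protocol 16.1 mentions multiple imputation as a possible sensitivity analysis, but the SAP does not take it up.

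Example Table 8 in SAP 5.1, titled "Completeness of primary outcome data by visit and treatment group", has a baseline row with columns for fully and partly missing forms. Section 5.2 extends that reporting to the secondary outcomes.

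**The concern.** Two kinds of missing data are treated alike. If the week-6 form is missing, the outcome is unknown. If only the baseline form is missing, the outcome is in hand and only a covariate is lacking. The complete-case rule discards the second group as well.

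Two things are at stake. First, 5.1.1 and 5.1.2 can then use different participants, so a difference between the two estimates could come from the change of population rather than from the adjustment. Second, baseline adjustment is meant to gain precision, and the lost participants can cost more than the covariate returns. SAP 2.6 reports 87 randomised against a target of 380, so observed outcomes are scarce.

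**Working it through.** **Inputs from the documents.** SD 10.7, target difference 4 points, 5% α, 10% β, at most 20% loss, 87 randomised (SAP 2.6); two-sided test (Protocol 16.1); 1:1 allocation (SAP 2.1).

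**Check on the plan's own figure.** With these inputs a two-sample t-test has power 0.8994 at 151 per arm and 0.9012 at 152. So 152 per arm is reproduced, and 152 / 0.8 = 190. The original sample size is not in dispute.

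**Assumptions, because the documents give no figure.**
- Week-6 scores: N = 70 (87 × 0.8 = 69.6), with 87 as the upper limit.
- Baseline to week-6 correlation: ρ from 0.1 to 0.5.
- Share of week-6 responders with no baseline: m from 5% to 15%, missing completely at random.

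**Step 1: large-sample rule.** The variance of complete-case ANCOVA relative to the unadjusted difference is (1 − ρ²)/(1 − m). It exceeds 1 when m > ρ². The SE ratio is the square root:
- ρ = 0.3, m = 10%: √(0.91/0.90) = 1.006
- ρ = 0.2, m = 15%: √(0.96/0.85) = 1.063
- ρ = 0.5, m = 10%: √(0.75/0.90) = 0.913
- m = 5%: 1.005, 0.979 and 0.889 at ρ = 0.2, 0.3 and 0.5

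If a missing baseline is set to the pooled mean, the SE ratio is about √(1 − ρ²(1 − m)). That gives 0.959, 0.983 and 0.880 for the first three settings.

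**Step 2: how many missing baselines tip the balance.** The 95% CI half-width of complete-case ANCOVA with M = N − k participants is t(M−3) × 10.7 × √(1 − ρ²) × √(4/M) × √(1 + 1/(M − 4)). The unadjusted half-width is 5.10 points with N = 70 and 4.56 with N = 87. The smallest k at which ANCOVA is the wider of the two is:

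| ρ | N = 70 | N = 87 |
|---|---|---|
| 0.2 | 2 | 3 |
| 0.3 | 6 | 7 |
| 0.4 | 10 | 13 |
| 0.5 | 16 | 21 |

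At ρ = 0.1 ANCOVA is marginally wider even with none missing, because the covariate explains almost nothing. With N = 70 and 7 missing, the half-width is 5.33 at ρ = 0.2 and 4.71 at ρ = 0.5.

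**Step 3: simulation of the three options.** N = 70, 3,000 runs per setting, mean 95% CI half-width in points:

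| ρ | m | Unadjusted | Complete-case ANCOVA | Pooled-mean baseline |
|---|---|---|---|---|
| 0.1 | 10% | 5.08 | 5.39 | 5.09 |
| 0.2 | 5% | 5.08 | 5.18 | 5.02 |
| 0.2 | 10% | 5.09 | 5.32 | 5.04 |
| 0.3 | 5% | 5.07 | 5.02 | 4.89 |
| 0.3 | 10% | 5.09 | 5.18 | 4.92 |
| 0.3 | 15% | 5.08 | 5.31 | 4.92 |
| 0.5 | 10% | 5.09 | 4.70 | 4.52 |
| 0.5 | 15% | 5.08 | 4.81 | 4.55 |

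The pooled-mean option is narrower than complete-case in every row. A separate simulation with a true 4-point difference (4,000 runs per setting) found it unbiased within simulation error, with 95% interval coverage of 0.948 to 0.954. The complete-case estimate was also unbiased under these assumptions.

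**Step 4: why the replacement is valid.** Protocol 13.7 requires the baseline forms before the first laser session, and Protocol 13.3 describes blinding of patients and staff. SAP 3.2 holds that allocation remained random despite the grid error. A baseline fill that ignores arm therefore carries no information about treatment, and no outcome value is altered.

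**The case against.** The strongest reply is that few baselines are likely to be missing. The forms are required before the first session, a research nurse administers the OMWQ-HN (Protocol 13.5), and a single answer of 0 to question 1 makes a complete score. The MDADI and EORTC multi-item scales are scored when at least half their items are present. Nothing in the documents supports a missing share of 10% or 15%. At 5%, complete-case ANCOVA still gains at ρ = 0.3 and 0.5. This stands, and it limits the size of the point. It does not remove it: one blank item voids an OMWQ-HN total above 0, and the MDADI global score and 11 H&N35 measures are single items that pro-rating cannot rescue.

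It is also true that the difference is small. At ρ = 0.3 and 10% missing, the fix shortens the half-width by 5.18 − 4.92 = 0.26 points on a 0 to 54 scale. With 70 scores every half-width computed stays above the 4-point target difference. The unadjusted estimate is reported as well, and Protocol 16.1 plans no hypothesis tests of secondary outcomes.

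Three stronger readings are tempting, and the documents support none of them:
- **Adjustment will lose precision in this trial.** That needs a missing share above about ρ², and neither quantity is given. The baseline row in Example Table 8 is an empty shell, not evidence that baselines were missing.
- **The complete-case ANCOVA is biased.** No bias is shown; under the assumptions used, all three estimators are unbiased.
- **The primary result is compromised.** Section 5.1.1 uses no baseline score.

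**Conclusion.** The point holds as a matter of efficiency and comparability. The rule discards observed outcomes for lack of a covariate and lets the adjusted and unadjusted estimates rest on different participants. It makes adjustment counterproductive if missing baselines exceed about ρ² of the week-6 responders. A low ρ is plausible because baseline precedes radiotherapy, but that is an inference.

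At 10% missing and ρ from 0.1 to 0.3, complete-case ANCOVA widens the half-width by roughly 0.1 to 0.3 points against no adjustment. At ρ = 0.5 it still narrows it. These figures rest on SD 10.7, 70 week-6 scores and baselines missing completely at random. If no baseline is missing, the rule changes nothing. The priority is optional to recommended.

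**What to change.** In SAP 5.1.2, and in both the MDADI and EORTC paragraphs of 5.2, replace the restriction to participants with both scores by wording such as:

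> All participants with the outcome score at the visit analysed (week 6, and 4 months where an adjusted difference is reported) are included. A baseline score that is still missing after any item-level pro-rating is replaced by the mean baseline score over both arms combined. The number replaced is reported for each arm.

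Add this to 3.2 and 5.5 as a stated exception to the complete-case rule, limited to baseline covariates. Without that addition those two sections would contradict the new text. Outcome scores remain unimputed.

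The cost is wording in five places and about one line of code per model. No new data are needed, and 5.1.1 does not change. In the settings simulated, the replacement was never less precise than complete-case analysis. Its worst showing against no adjustment was at ρ = 0.1 and 15% missing, with a half-width of 5.11 against 5.09.

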5.2 Secondary outcomes

For all secondary outcomes the data completeness will be described as outlined for the primary outcome in Example Table 8.

WHO Mucositis Oral Toxicity Scale:

Data will be summarised descriptively as the frequency and percentage of each grade at each time point for each of the treatment groups. Due to the achieved number of participants in the study it may be necessary to collapse categories in order to present more meaningful summaries. The difference between treatment groups in the percentage of participants with grade III or IV (severe or life-threatening) at week 6 will be reported with 95% confidence interval. This categorisation was proposed in the protocol and has been reported in a previous study [12]. A 95% confidence interval for the difference at 4 months will also be reported if appropriate.

M.D. Anderson Dysphagia Inventory (MDADI):

One emotional subscale item (“I do not feel self-conscious when I eat”) and one functional subscale item (“I feel free to go out to eat with my friends, neighbours, and relatives”) will be reverse scored in accordance with the scoring guideline [3]. Each subscale (global, emotional, functional, and physical) will be calculated as an average of its items, and then multiplied by 20 in order to rescale the scores to be from 20 (worst impairment) to 100 (no impairment). A subscale score will only be calculated if at least half of its items are non-missing.

The 19-item total/composite score will also be used to summarize overall impairment based on the weighted average of the raw (i.e., before rescaling) physical, functional, and emotional subscale scores [13]. The total/composite score will then be multiplied by 20 to rescale the range to be from 20 (worst impairment) to 100 (no impairment). All three subscale scores must be non-missing for the total/composite score to be calculated.

Data on the global, emotional, functional, physical, and total/composite scores will be summarised descriptively as mean, standard deviation, median, interquartile range and range at each time point for each of the treatment groups. The difference between treatment group mean total/composite score and mean global score at week 6 adjusted for the baseline of the score will be reported with 95% confidence intervals (only if the assumptions of the ANCOVA model are satisfied). This will be on a complete case basis for those participants with a score at both baseline and 6 week visit. A 95% confidence interval for the difference at 4 months will be reported if appropriate.

EORTC-QLQ-C30 (version 3.0) and EORTC-QLQ-H&N35 (version 3.0):

Procedures for scoring the scales and items of the QLQ-C30 and H&N35 will be in accordance with the published scoring manual [6]. Therefore, a scale’s score will only be calculated if at least half of its items are non-missing. The QLQ-C30 summary score will be computed as the mean of 13 scores from the QLQ-C30 (excluding the global health/QoL and financial difficulties scores) [7]. The symptom scales/items that form part of the summary score will be reverse scored first to ensure that higher scores on the summary score reflect better outcomes.

Data on the 21 outcome measures will be summarised descriptively as mean, standard deviation, median, interquartile range and range at each time point for each of the treatment groups. The difference between treatment group means for each of the 21 outcome measures at week 6 adjusted for the baseline of the outcome measure will be reported with 95% confidence intervals (only if the assumptions of the ANCOVA model are satisfied). This will be on a complete case basis (after pro-rating) for those participants with a score at both baseline and 6 week visit. A 95% confidence interval for the difference at 4 months will also be reported if appropriate.

Performance Status Scale for Head and Neck Cancer patients (PSS-HN):

Data will be summarised descriptively, by subscale, as the frequency and percentage of each score category at each time point for each of the treatment groups. Given there were only 87 patients randomised in total and the frequency tables will have either 22 cells (11 categories by 2 treatment groups) or 10 cells (5 categories by 2 treatment groups) it may be necessary to summarise the data as the frequency and percentage of participants scoring ≤ 50 for the subscale [14, 15]. As these subscales are made up of ordinal categories, the median and range will also be presented.

Oral intake and tube dependency:

Data on the oral intake, feeding tube dependency, whether enteral feeding was initiated, and type of feeding tube will be summarised descriptively as the frequency and percentage at each time point for each of the treatment groups. Data on the number of days the feeding tube was used in the past week will be described using appropriate summary statistics.

Weight and Body Mass Index (BMI):

BMI scores at each time point will be calculated using height data collected at baseline and weight collected at each time point. Data on weight and BMI will be summarised descriptively as mean, standard deviation, median, interquartile range, observed range at each time point for each of the treatment groups.

Timed water swallow test (WST):

Measures of swallow capacity (mL/time taken), swallow volume (mL/number of swallows), and swallow speed (time taken/number of swallows) will be derived from the data.

Data on swallow capacity, volume, and speed will be summarised descriptively as mean, standard deviation, median, interquartile range, observed range at each time point for each of the treatment groups.

Pain outcomes

OMWQ-HN will be summarised numerically as mean, standard deviation, median, interquartile range, and range at each time point (baseline to week 6) for each of the treatment groups [as above].

EQ-5D-5L pain/discomfort domain will be summarised as median, interquartile range, and range [16].at baseline and week 6 only for each of the treatment groups

Analgesics, topical treatment, and visits to oral hygienist (other than for laser treatment)

The number of visits to an oral hygienist over the past seven days will be summarised descriptively as median, interquartile range, and range at each time point for each treatment group. The remaining data will be summarised descriptively as the frequency and percentage at each time point for each of the treatment groups. Data on analgesics will be categorised as no analgesia, simple analgesia (e.g., ibuprofen, paracetamol), opioids (e.g., morphine, oxycodone), and others. Data on mouthwash will be categorised as simple (e.g. FluoriGard, saline, sodium bicarbonate), analgesic (e.g., Difflam), antiseptic (e.g. chlorhexidine), mucosa protecting mouthwash (e.g. Mugard, Gelclair, Caphasol), and others.

Disease outcomes:

Data on disease outcomes collected at 14 months will be summarised descriptively as the frequency and percentage for each of the treatment groups.

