Quality adjusted survival analyses will be carried out to simultaneously assess quality and survival functions. A Quality function, based on the EQ5D global score, will be estimated at each survival event time using interpolation, and the survival distribution down-weighted by any negative quality function. The area under each of the survival and quality adjusted survival curves will be presented as (with 95%CI).

Long term data will be presented graphically including proportions of positive and negative changes from baseline. Standardised area under the curve analysis will be used to describe longitudinal quality of life scores. Exploratory, descriptive hierarchical modelling, not based on significance testing, may be used to explore repeated measures nested within patients accounting for important baseline clinical confounders and stratification factors.

Hypothesis testing is not planned for the analyses of secondary outcome measures.

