APPENDIX 2: WHO Mucositis Oral Toxicity Scale

Reference:

WHO: http://www.who.int/en/ WHO Handbook 1979, pp.15-22. Sonis et al. Cancer 2004; 100(9 Suppl):1995-2025.

The World Health Organization has developed a grading system for mucositis based on clinical appearance and functional status.

The WHO scale is dependent on both objective and subjective variables, and measures anatomical, symptomatic as well as functional components of oral mucositis.

WHO Oral Mucositis Grading Scale

Grade	Description
0 (none)	None
I (mild)	Oral soreness, erythema
II (moderate)	Oral erythema, ulcers, solid diet tolerated
III (severe)	Oral ulcers, liquid diet only
IV (life-threatening)	Oral alimentation impossible

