1.2.2 Secondary objectives

- Determine the effectiveness of LLLT in preventing severe OM during RT or CRT for HNC as measured by WHO mucositis scores.
- Apply evidence derived from the trial to inform NHS guidance in the use of LLLT for managing OM.
- Investigate the short and long term benefits to patients in terms of dependence on feeding tubes, nutritional status, pain control, admission to hospital, treatment interruptions and swallowing function and quality of life.

- Investigate the long term risks of LLLT (survival, recurrence, disease progression).
- Identify barriers and facilitators to implementing LLLT in routine clinical care through a qualitative process evaluation.

See protocol version 4.0 for further objectives associated with the economic and qualitative sub studies.

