2.4.2 Secondary outcome measures

Note: Data for any 14 month outcomes (marked with asterisk) were only collected for participants who commenced laser therapy prior to 6th July 2018.

WHO Mucositis Oral Toxicity Scale:

The World Health Organisation has developed a grading system for mucositis [2] which measures objective, subjective and functional aspects of OM based on clinical appearance and functional status. The WHO scale is scored on a five point scale, with 0 indicating none, 1 indicating mild, 2 indicating moderate, 3 indicating severe, and 4 indicating life-threatening OM.

The WHO scale was collected by the clinician at baseline, weekly during weeks 1 to 6 of treatment, and at 4 month follow-up.

M.D. Anderson Dysphagia Inventory (MDADI):

The MDADI [3] is patient-reported swallowing outcome measure, specifically designed for the HNC population. The MDADI contains 20 items. Each item on the MDADI follows a five-point response scale ranging from 1 (strongly agree) to 5 (strongly disagree). The MDADI is comprised of four subscales: global (1 item); emotional (6 items); functional (5 items); and physical (8 items). Five scores can be calculated from the MDADI including 2 summary scores (global, total/composite) and 3 subscales (emotional, functional, physical) each calculated as an average with a range of 20 (worst impairment) to 100 (no impairment). The 19-item total (or composite) score will be used to summarize overall impairment on the basis of physical, functional, and emotional domains.

The MDADI was collected at baseline, week 6 of treatment, and at 4 month and 14 month follow-up*.

EORTC-QLQ-C30 (version 3.0) and EORTC-QLQ-H&N35 (version 3.0):

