Modified Intention-to-treat (mITT) analysis set: This population contains all patients randomised into the study (regardless of their adherence with the entry criteria, regardless of subsequent withdrawal from treatment or deviation from the protocol). However, it is a modified ITT analysis set because it will include participants in the treatment group corresponding to the treatment they randomly received (where the randomised (x,y) coordinates for seven participants were used to generate an allocation from the wrong grid).

Statistical analyses will be conducted on complete cases from the mITT analysis set. Participants will be included in analyses if they attended the visit of interest and have evaluable data for the outcome measure of interest. Evaluable data here is non-missing for all outcome measures listed in Section 2.4 except the three questionnaires MDADI, QLQ-C30 and H&N 35, where simple imputation for missing questionnaire items in accordance with the questionnaire’s scoring manual will be used.

Safety population: For the analysis of safety data all randomised patients who received at least one session of laser therapy will be included.

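### The only on-treatment between-arm estimate of severe mucositis is prevalence at week 6, while the objective is prevention during RT or CRT; an ever-severe contrast for weeks 1-6 should be added

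*SAP*

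**What the plan says.** The first secondary objective in SAP 1.2.2, worded identically in protocol 9.2, is: "Determine the effectiveness of LLLT in preventing severe OM during RT or CRT for HNC as measured by WHO mucositis scores". On data collection, SAP 2.4.2 states: "The WHO scale was collected by the clinician at baseline, weekly during weeks 1 to 6 of treatment, and at 4 month follow-up". Protocol Appendix 2 defines grade III as "Oral ulcers, liquid diet only" and grade IV as oral feeding being impossible.

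SAP 5.2 plans three outputs for this scale:

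- A table by visit and arm: "Data will be summarised descriptively as the frequency and percentage of each grade at each time point for each of the treatment groups".
- The treatment-period contrast: "The difference between treatment groups in the percentage of participants with grade III or IV (severe or life-threatening) at week 6 will be reported", with a 95% confidence interval.
- A later, conditional contrast: "A 95% confidence interval for the difference at 4 months will also be reported if appropriate".

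The rule on missing data is in SAP 3.2 and is repeated in 5.5: "Participants will be included in analyses if they attended the visit of interest and have evaluable data for the outcome measure of interest". Item imputation is allowed for MDADI, QLQ-C30 and H&N35 only, so none applies to the WHO grade. The SAP plans no ever-severe, worst-grade, time-to-severe or duration summary of the WHO score.

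**The concern.** Whether severe mucositis was prevented during a course of treatment is most naturally read as whether a patient ever reached grade III or IV in that course. The planned contrast asks whether a patient is at grade III or IV at one visit. The two answers differ for two kinds of patient:

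- One who is severe in, say, week 5 and has improved to grade II by week 6 counts as non-severe.
- One who is severe in week 5 and has no week-6 score leaves the comparison, whatever the earlier grades.

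If laser shifts the timing of severe mucositis, a single-visit prevalence can also give a different picture from the proportion ever affected. At stake is what the trial can say about its own stated objective. The primary analysis and the sample size are not affected.

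**Working it through.** **Does any planned output give the number ever severe?** The documents state no figure for the WHO outcome, so there is none to reproduce. The sample size in SAP 2.6 concerns OMWQ-HN only. The candidate outputs are:

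| Planned output | Gives the number ever severe in weeks 1-6? |
|---|---|
| Week-6 difference with CI (SAP 5.2) | No: one visit, complete cases |
| 4-month difference with CI, conditional (SAP 5.2) | No: after treatment |
| Grade by visit and arm (SAP 5.2) | No: six marginal percentages do not show which patients overlap |
| Adverse events by worst grade since day 1 (SAP 6.1) | No: graded on CTC 4.0, not the WHO scale named in the objective |

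**How many patients could the week-6 contrast miss?** The documents give no weekly severe rates or week-to-week correlations, so these are assumptions. Each patient has a latent normal series over six weeks with correlation ρ^|i−j| between weeks i and j. A patient is severe in week w when the latent value is below the normal quantile of that week's assumed prevalence. Then P(severe earlier, not at week 6) = P(ever severe in weeks 1-6) − P(severe at week 6).

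*Prevalence levelling off, 2/8/20/35/45/45% in weeks 1-6:*

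| ρ | Week 6 | Ever severe | Severe earlier, not at week 6 |
|---|---|---|---|
| 0.6 | 45% | 70% | 25% |
| 0.7 | 45% | 65% | 20% |
| 0.8 | 45% | 61% | 16% |
| 0.9 | 45% | 55% | 10% |
| 0.95-0.97 | 45% | 49-51% | 4-6% |

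*Prevalence still rising, 2/8/15/25/35/45%:* with ρ of 0.9-0.97, severe earlier but not at week 6 is 1-5%.

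The overall range is about 1-25%. In patients: 0.01 × 87 = 0.9 and 0.25 × 87 = 21.8, so roughly 1 to 22 of the 87 randomised.

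In the levelling-off scenario with ρ of 0.6-0.9, about 58-80% of patients severe in weeks 1-5 are still severe at week 6. Most are therefore classified as severe by the planned contrast.

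**Would the between-arm difference change?** Again on assumed rates:

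- *Laser lowers prevalence throughout.* Sham 1/5/15/30/45/50%, laser 1/3/8/18/28/35%, ρ of 0.5-0.97. At week 6 the difference is 50 − 35 = 15 points. Ever severe is 52-73% on sham and 36-55% on laser, a difference of 16-18 points.
- *Laser mainly delays onset.* Same sham rates, laser 1/2/5/12/25/48%. At week 6 the difference is 50 − 48 = 2 points. Ever severe gives 65.6 − 53.9 = 11.7 points at ρ = 0.7 and 56.0 − 48.8 = 7.2 points at ρ = 0.9.

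**Precision.** The 95% half-width for a difference in proportions is 1.96 × √(2p(1−p)/n). With 87 randomised 1:1 there are about 43 per arm:

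- n = 43, p = 0.5: 1.96 × √(0.5/43) = 21 points; p = 0.3 or 0.7: 19 points.
- n = 35 (assumed evaluable), p = 0.5: 23 points; p = 0.3 or 0.7: 21 points.

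Either contrast would have an interval of about ±20 points.

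**The case against.** The case for leaving the plan alone has several parts.

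*Week 6 is a coherent choice.* The primary outcome and the MDADI and EORTC contrasts use the same visit, which limits the number of contrasts in a trial of 87. The objective does not say cumulative incidence in so many words. This supports keeping the week-6 contrast. It does not make that contrast an estimate of prevention during treatment.

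*The outcome is secondary and imprecise.* Protocol 16.1 says these comparisons are not powered, and adds: "Hypothesis testing is not planned for the analyses of secondary outcome measures". In the first scenario above, the two contrasts differ by only 1-3 points. In both scenarios every difference lies within the interval half-width. This limits the weight of the point. But where estimation is all that is planned, the quantity estimated should match the objective.

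A reader might also infer three stronger things that the documents do not support:

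- *That everyone severe in weeks 1-5 is counted as non-severe or missing.* Those still severe at week 6 are counted correctly; only those who improved or have no week-6 score are affected.
- *That the data from weeks 1-5 are discarded.* They are tabulated by grade and arm at every visit, and a shift in onset could be seen there, though without an estimated difference or a count of patients ever severe.
- *That week 6 loses the sickest patients.* This is plausible, since protocol 14.1 foresees sessions missed through infection or inability to attend. But no document gives week-6 WHO missingness or links it to severity. Protocol 13.6 gives the week-6 assessment a window of one week either side, protocol 14.1 asks for data wherever possible, particularly from in-patients, and SAP 5.2 describes completeness for every secondary outcome.

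**Conclusion.** The concern holds as a mismatch between objective and estimate. The only on-treatment between-arm estimate of severe WHO mucositis with a confidence interval is complete-case prevalence at week 6, and no planned output gives the number of patients ever severe during weeks 1-6. That much follows from the text alone.

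The size rests wholly on assumed prevalences and correlations. About 1-25% of participants would be severe earlier but not at week 6, near the bottom of the range if severity persists once reached or is still rising at week 6, and near the top if it fluctuates. The effect on the between-arm difference may be small, or several points if laser mainly delays onset. It is a worthwhile, inexpensive improvement to a secondary analysis.

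**What to change.** In SAP 5.2, under the WHO scale:

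1. Add the between-arm difference, with 95% CI, in the percentage of participants with any WHO grade III or IV in weeks 1-6, alongside the week-6 contrast.
2. Count a participant as severe if any available weekly score is III or IV, and report the number of weeks assessed per arm.
3. Add a sensitivity analysis for participants with missed weeks and no severe grade seen, for example restricted to those with all or nearly all weekly scores. State the denominator.
4. Label the existing contrast as prevalence at week 6.

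The cost is SAP wording, one derived variable and the sensitivity analysis; no new data are needed. There are two downsides. Participants with missed weeks may be under-counted as severe, which would favour the arm with more missed visits, hence items 2 and 3. It also adds one more unpowered secondary estimate, to be reported without a hypothesis test like the others.
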